### **9.2.1. Ramucirumab Dosing Schedule**

Ramucirumab will be dosed at 8 mg/kg and administered as a 1-hour IV infusion prior to the administration of LY2875358 on Days 1 and 15 of a 28-day cycle in Part A and B of this study. The infusion rate of ramucirumab should not exceed 25 mg/min.

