It is recognized that, in the course of clinical cancer care, it is not always possible to schedule therapeutic infusions precisely 2 weeks following a prior infusion (ie, because of holidays, travel difficulties, or other circumstances). Accordingly, study drug infusions administered within the timing window as indicated in the Study Schedule (see [Attachment 1](#)) relative to the regularly scheduled Q2W treatment time point will be considered acceptable. Moreover, in Cycle 3 or beyond, ramucirumab and LY2875358 dosing may be delayed for up to approximately 14 days because of holidays, weekends, inclement weather, or other justifiable events, and not counted as a protocol violation. This approximate up to 14-day time period begins on the day that the next dose of study treatment should have been administered. In order to keep the administration of both study drugs synchronized, the next dose of ramucirumab and LY2875358 should be administered at the same study day to continue the regularly scheduled Q2W treatment time points.

In the event of dosing delays or missed doses, disease assessment and imaging studies should be undertaken according to the original study schedule, regardless of the actual number of on-study treatments received.

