Radiological Tumor Assessment g	X										Every 6 weeks after initiation of study treatment; after Cycle 9 every 2-4 cycles as clinically indicated	
Functional Tumor Imaging	X h										FDG-PET mandatory in Part B1 (gastric) 6 weeks after initiation of study therapy	

Abbreviations: CNS = central nervous system; CT = computed tomography; CTCAE = Common Terminology Criteria for Adverse Events; DCE-MRI = dynamic contrasted-enhanced magnetic resonance imaging; ECG = electrocardiogram; ECOG = Eastern Cooperative Oncology Group; FDG-PET = 2-deoxy-2[F-18]fluoro-D-glucose positron emission tomography; FLT-PET = 3-deoxy-3[F-18]fluorothymidine positron emission tomography; fT4 = free thyroxine; PD = pharmacodynamics; PET = positron emission tomography; PK = pharmacokinetics; TSH = thyroid-stimulating hormone; V = visit.

a Short-term follow-up begins on the day after the patient's last dose of study drug and ends approximately 30 days later. This visit should be scheduled  $30 \pm 3$  days after last dose of study drug.

b Electrocardiograms must be recorded before any study drug is administered. In Cycle 1, Day 1 and 15 only, additional ECGs must be recorded pre- and post-LY2875358 infusion, immediately before collecting the corresponding PK samples.

- c Local hematology, coagulation tests, and urinalysis may be done within 2 days prior to administration of study drugs (except Cycle 1, Day 1 [within 3 days]). An additional local chemistry panel according to local standard of care may be done and used for on-study dosing decisions; if done so, chemistry testing must also still be performed by the central laboratory at the regularly scheduled time points. The central chemistry laboratory results will be used for patient eligibility and subsequent safety analyses. In exceptional cases, patient may be enrolled based on local chemistry results after discussion with the sponsor if central laboratory samples results required for eligibility are not available in a timely manner (e.g., due to inclement weather conditions).
- d If, while receiving the investigational product(s), a patient has proteinuria  $\geq 2+$  per a dipstick or routine urinalysis test, a 24-hour urine collection will be conducted prior to the subsequent scheduled treatment (see Section 9.2.3.2.2).
- e Samples will be collected at Cycle 3, Cycle 5, Cycle 7, Cycle 9, and every 4 cycles thereafter while patient is on study treatment.

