- f If a patient experiences an infusion-related reaction (see Section 9.2.3.1), immunogenicity samples for anti-ramucirumab and anti-LY2875358 antibodies and PK samples will be taken as close to the onset of the event as possible, at the resolution of the event, and approximately 30 days following the event.
- g The method of assessment used at baseline must be used consistently for tumor assessment and will be repeated approximately every 6 weeks ( $\pm 7$  days) during the study treatment period for lesions outside the CNS. For those patients with known CNS metastases, ongoing CNS surveillance using the same modality is required approximately every 12 weeks ( $\pm 7$  days). Positron emission tomography /CT is allowed if CT portion is of diagnostic quality.
- h For patients in Part B1 (gastric), the mandatory FDG-PET approximately 6 weeks ( $\pm 7$  days) after initiation of study treatment should be performed only if the baseline FDG-PET demonstrated PET avid lesion(s). Further functional tumor imaging (including but not limited to DCE-MRI, FLT-PET) is permitted throughout the study in all patients if appropriate for the respective tumor type at the discretion of the investigator and considered as institutional standard of care or is part of an appropriate imaging study open at the site.

---

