6.12. Efficacy Analyses

As a coprimary objective for Part B, this study will evaluate preliminary antitumor activity observed with ramucirumab in combination with LY2875358 in the tumor-specific expansion cohorts.

Overall Response Rate (ORR): ORR is defined as the proportion of patients who exhibit a confirmed CR or PR relative to baseline as defined by RECIST 1.1 (Eisenhauer et al. 2009).

ORR is computed as the number of responders divided by the total number of treated patients. A responder is defined as any patient who exhibits a confirmed CR or PR relative to baseline

assessment, done on or up to 7 days prior to Cycle 1 Day 1. Patients with response that is deemed not evaluable will be considered non-responders and will be included in the denominator for the purpose of calculating ORR. ORR will be assessed within each cohort, ORR with 95% CIs will be estimated using the Clopper-Pearson method.

Progression-Free Survival (PFS): The PFS time is measured from the date of receiving the first dose of study drug to the date of first objective progression as assessed by the investigator or the date of death due to any cause, whichever is earlier. Table 6.2 provides additional details. The censoring is taken in the following order:

- If a patient does not have a complete baseline disease assessment, then the PFS time will be censored at the enrollment date, regardless of whether or not objectively determined disease progression or death has been observed for the patient; otherwise,
- If a patient is not known to have died or have objective progression as of the data inclusion cutoff date for the analysis, the PFS time will be censored at the last evaluable objective progression-free disease assessment date.

If a patient has a missed visit prior to an event (progression or death), then the PFS time will be censored at the last evaluable assessment prior to the event.

Table 6.2. Definition of PFS

Situation	Outcome	Date of Progression or Censoring
Death before first objective PD assessment	Progressed	Date of death
Objective PD	Progressed	Date of first radiologic assessment showing progressive disease
No evaluable baseline tumor assessments	Censored	Enrollment date
No progression	Censored	Date of last radiologic assessment of measured lesions showing no progression
New systemic anticancer treatment started	Censored	Date of last radiologic assessment of measured lesions showing no progression prior to the commencement of new systemic anticancer treatment

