Death or progression after more than one missed visit (after 3 months since last assessment)	Censored	Date of last radiologic assessment of measured lesions showing no progression prior to the missed visit

The date of first documented objective disease progression must be recorded on the CRF even if it occurs after the patient has started a new therapy.

Disease Control Rate (DCR): The proportion of patients in the analysis population who exhibit an SD or confirmed CR or PR relative to baseline during the study. Response is defined by RECIST 1.1 (Eisenhauer et al. 2009).

Change in Tumor Size (CTS): The change in tumor size from baseline to the measurement with the smallest tumor size during the study period. Change in tumor size will be assessed in each patient using radiographic imaging. The tumor size of target lesions will be determined as defined by RECIST 1.1 (Eisenhauer et al. 2009).

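### The 3-month limit in the PFS missed-visit rule fits only the 6-week scan schedule, so progressions found at permitted 4-cycle scans after Cycle 9 may be censored

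*SAP*

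**What the plan says.** SAP Section 6.12 gives the missed-visit rule for PFS twice.

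- Table 6.2 censors "Death or progression after more than one missed visit (after 3 months since last assessment". The censoring date is "Date of last radiologic assessment of measured lesions showing no progression prior to the missed visit".
- The sentence just above the table reads "If a patient has a missed visit prior to an event (progression or death), then the PFS time will be censored", with the date set back to the most recent evaluable scan. This asks for one missed visit and sets no time limit.

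Protocol Attachment 1 (During- and Post-study Assessments) also gives the scan schedule twice.

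- Comment to the radiological assessment row: "Every 6 weeks after initiation of study treatment; after Cycle 9 every 2-4 cycles as clinically indicated".
- Footnote g to that row: "The method of assessment used at baseline must be used consistently for tumor assessment and will be repeated approximately every 6 weeks", with a window of ±7 days, "during the study treatment period for lesions outside the CNS". It makes no exception after Cycle 9.

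Protocol Section 9.2.1 sets dosing "on Days 1 and 15 of a 28-day cycle". Under Section 9.2.3, when doses are delayed or missed, "disease assessment and imaging studies should be undertaken according to the original study schedule". Neither document defines a missed visit, and neither says whether the bracketed 3 months explains the phrase before it or adds a second condition.

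**The concern.** A missed-visit rule is meant for patients whose progression date is uncertain because scheduled scans were not done. Here the limit is a fixed calendar time that suits one scan interval, and the protocol allows a longer interval later on. A patient on the longest permitted interval could follow the schedule comment exactly, progress at the next scan, and still be returned to the previous clean scan as censored. A death more than 3 months after the last scan would be handled in the same way.

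Such censoring is informative, because it is triggered only when an event occurs. It acts in one direction, towards longer PFS. The trial has no control arm in which the same bias would cancel, and SAP Table JTBF.5.3 sets out historical median PFS values beside which the results will naturally be read.

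**Working it through.** **Inputs.** Limit of 3 months (SAP Table 6.2). Scans every 6 weeks, ±7 days (footnote g). Scans every 2 to 4 cycles after Cycle 9 (Attachment 1 comment). Cycle of 28 days (Protocol 9.2.1). Reference medians of 2.1 (gastric), 4 (HCC), 7.1 (RCC) and 3 (NSCLC) months (SAP Table JTBF.5.3). Landmarks of interest: 60% at 12 weeks (gastric) and 75% at 4 (HCC), 7.1 (RCC) and 3 months (NSCLC) (Protocol Table JTBF.2). One month = 365.25/12 = 30.44 days.

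**Step 1: reproduce the 3 months.** 3 × 30.44 = 91.3 days. Two 6-week intervals plus the window: 2 × 42 + 7 = 91 days = 2.99 months. The figure is right for the 6-week schedule.

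**Step 2: apply it after Cycle 9.** Cycle 9 ends at 9 × 28 = 252 days = 8.28 months, which is also the sixth 6-weekly scan (6 × 42). I assume the ±7 days carries over to the longer intervals.

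| Spacing | Day since last scan (±7) | Beyond 91.3 days? | 6-weekly scans missed at the nominal day, by footnote g | Two intervals + 7 days |
|---|---|---|---|---|
| 2 cycles | 56 (49–63) | No | 1 (day 42) | 119 days, 3.9 months |
| 3 cycles | 84 (77–91) | No, but at the limit | 1 (day 42) | 175 days, 5.7 months |
| 4 cycles | 112 (105–119) | Yes, throughout | 2 (days 42 and 84) | 231 days, 7.6 months |

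The 56-day scan counts as a miss under footnote g because the day-42 window closes at day 49.

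**Step 3: is a progression at a permitted scan counted?**

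| Reading of the rule | 2 cycles | 3 cycles | 4 cycles |
|---|---|---|---|
| More than one miss required, counted against the Attachment 1 comment | Event | Event | Event |
| 3 months alone | Event | Event | Censored |
| More than one miss and 3 months, counted against footnote g | Event | Event | Censored |
| One miss (sentence above the table), counted against footnote g | Censored | Censored | Censored |

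**Step 4: how many patients are exposed?** With exponential PFS, the share still event-free at 8.28 months is 0.5^(8.28/median), or s^(8.28/t) for a landmark of s at t months.

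| Cohort | At reference median | At landmark of interest |
|---|---|---|
| Gastric/GEJ | 0.065 | 0.216 |
| NSCLC | 0.148 | 0.452 |
| HCC | 0.238 | 0.551 |
| RCC | 0.446 | 0.715 |

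For RCC at the benchmark, 0.446 is about 7 of 15 or 20 of 45 patients.

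**Step 5: worst case, every scan after Cycle 9 at 4 cycles.** All later progressions are censored, so a Kaplan-Meier curve stays flat from day 252. The next scan is at 252 + 112 = 364 days = 11.96 months.

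- RCC, median 7.1 months: PFS at day 364 should be 0.5^(11.96/7.1) = 0.31 and would read 0.45. The curve is already below 50% at day 252, so the median does not change.
- RCC, 75% at 7.1 months: the implied median is 7.1 × ln 2 / ln(1/0.75) = 17.1 months, seen at the scan on day 252 + 3 × 112 = 588 (19.3 months). PFS at day 364 should be 0.75^(11.96/7.1) = 0.62 and would read about 0.71. The median would read as not reached.
- HCC, 75% at 4 months: the implied median is 9.6 months, seen at day 364 (12.0 months). It too would read as not reached, with the curve flat at about 0.55.

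Simulation of 20,000 patients per scenario agrees to within 0.005 on these PFS values and shows no change at 2- or 3-cycle spacing on the 3-month test.

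**The case against.** The strongest reply is that the row is conditioned on missed visits. The 3 months stands in brackets, and the censoring date is tied to the missed visit. A patient on a permitted 4-cycle interval has missed none, so that date has no meaning and the objective-progression row of Table 6.2 applies. This is a fair reading, and a reader who infers from the table that every event beyond 3 months is discarded goes further than the text does.

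It does not settle the matter. After Cycle 9 the comment leaves timing to clinical indication, so there is no fixed visit against which to count a miss, and the 3 months is the only part that can be programmed directly. Footnote g is also in force, and by its count the 4-cycle patient has missed two scans, so both conditions are met. If sites do scan every 6 weeks throughout, the problem disappears. It arises when sites follow the comment and the analysis counts by the footnote or by the 3 months.

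Other parts of the reply stand. On the 3-month test, 2- and 3-cycle spacing within the window is safe. Uniform 4-cycle spacing is a worst case. A reader might also infer that median PFS is biased upward in general, most of all in RCC. The documents do not support that, because all four reference medians fall before 8.3 months. PFS is not the co-primary endpoint, the analyses are descriptive, and SAP Section 6.12 does not name a Kaplan-Meier median (the method appears only in the reference list).

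**Conclusion.** The point holds as a mismatch that should be corrected before PFS is analysed. The 3-month limit was not adapted to the longer scan intervals, and whether a progression at a permitted 4-cycle scan counts depends on which of two schedules and which of two missed-visit rules is applied.

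Under the 3-month test, or when more than one miss is counted against footnote g, only 4-cycle spacing is affected. Under the single-miss sentence read with footnote g, 8- and 12-week spacing could lose events as well. For scans following the post-Cycle-9 comment, the bias begins after 8.3 months, raises the late curve, and raises the median only where the true median exceeds about 8.3 months. Its size runs from zero to the worst case shown, which assumes exponential PFS, Kaplan-Meier estimation, uniform 4-cycle scans and no other censoring.

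ORR is unaffected. The expansion landmarks, at most 7.1 months, are not reached by the 3-month limit after Cycle 9. That assurance does not extend to the conflict between one and more than one missed visit, which can arise at any scan.

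**What to change.** In SAP Section 6.12:

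1. Define a missed assessment as a scheduled scan not done within its window.
2. Censor only when two or more consecutive scheduled assessments, at the interval in force at that time, were missed before the event.
3. Remove the fixed 3 months, or limit it to the 6-week period.
4. Make the sentence above Table 6.2 agree with the table.

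In Protocol Attachment 1, reconcile the schedule comment with footnote g on scan frequency after Cycle 9, so that the SAP can refer to one schedule. No progression at a scan done on schedule would then be censored by the rule.

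The cost is a few lines in the SAP and a clarification of the protocol schedule. Late PFS may read slightly less favourably.

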6.13. Bioanalytical and Pharmacokinetic/Pharmacodynamic Methods

6.13.1. PK/PD Analyses

Pharmacokinetic analyses will be conducted on patients who have received at least 1 dose of study drug(s) and have had samples collected.

Population PK models for LY2875358 and ramucirumab may be developed using nonlinear mixed effect modeling. The LY2875358 PK data from this study may be added to data available from other studies, such as the Phase 1 Study JTBA, and the base model for LY2875358 will be the previously developed Target-mediated drug disposition (TMDD) model. Noncompartmental methods may also be used if warranted by the data.

The parameters for ramucirumab will include steady-state maximum ($C_{ss,max}$) and steady-state minimum ($C_{ss,min}$) and area under the concentration-time curve during the dosing interval at steady state ($AUC_{\tau,ss}$).

The parameters for LY2875358 may include systemic clearance (CL), volume of distribution (V), $C_{ss,min}$, or TMDD model parameters, such as receptor-mediated clearance, non-receptor-mediated clearance, volume of the central compartment, and volume of the peripheral compartment.

Additional exploratory analyses will be performed if warranted by data. These exploratory analyses may include:

- Evaluating the relationship between PK and antitherapeutic antibodies
- Evaluating the relationship between PK and biomarkers, such as MET ECD
- Evaluating the relationship between exposure and response in terms of safety and efficacy (eg, incidence of adverse reactions, ORR, change in tumor size).

The version of any software used for the analysis will be documented, and the program will meet the Lilly requirements of software validation. It is possible that other validated equivalent PK software programs may be used if appropriate, warranted, and approved by Global Pharmacokinetic Management.

6.13.2. Biomarker Analyses

Protocol section 10.2.2 provides a description of the biomarker samples that may be used to carry out biomarker-specific exploratory analyses as mentioned in Section 4.3. Planned exploratory analyses will include, but are not limited to, known or hypothesized biomarkers that

are related to VEGF and MET signaling pathways, or tumor biology of the respective tumor types enrolled or associated with sensitivity/resistance to the study drugs.

Across all parts of the study, blood and tissue samples specified (including post-progression and/or archived tumor samples) may be analyzed to explore potential biomarker(s) associated with response to treatment. Somatic mutation status and/or copy number variations of genes that are targets of the study drug(s), known to be risk factors for cancer, or associated with resistance to anticancer therapies will be analyzed at a laboratory designated by the sponsor. This analysis may employ targeted or whole-exome sequencing approaches.

In Parts B1, B2, B3, and B4 of the study, tumor-specific (gastric, hepatocellular, or renal cell cancers) biomarker results based on immunohistochemical (IHC), fluorescence in-situ hybridization (FISH), polymerase chain reaction (PCR), or other means for detection and quantitation of cancer-associated protein or nucleic acid changes may be investigated with the aim of identifying genetic variation(s) and/or variations in protein expression that are associated with favorable clinical response within each tumor type or more broadly across multiple tumor types.

All biomarkers will be specifically investigated with the aim of developing a patient stratification strategy that will enable defining a target patient population that is more likely to respond to the treatment regimen being investigated and/or less likely to suffer from TEAEs.

Where applicable, the above associative/correlative assessments involving clinical response and biomarker data may be extended or adjusted to include relevant safety, toxicity, and PK/PD endpoints.

6.14. Subgroup Analyses

As subgroup analyses, co-primary endpoints for Part B will be analyzed for the potential prognostic factors such as

- Tumor types (Part B1: Gastric or GEJ adenocarcinoma; Part B2: Hepatocellular cancer (HCC); Part B3: Renal cell carcinoma (RCC, any histology)); Part B4: Non-small cell lung cancer (NSCLC, squamous or non-squamous))
- Age (<= 65 years vs. > 65 years)
- Sex (male vs. female)
- ECOG performance status (0,1 vs 2 in part A and 0 vs 1 in part B)

6.15. Protocol Violations

All significant protocol deviations will be listed by parts (Part A, Part B1, B2, B3 and B4) and by reasons (e.g., inclusion/exclusion criteria, noncompliance with protocol procedures, informed consent/assent process etc.).

6.16. Interim Analyses and Data Monitoring

An interim analysis will be performed after completion of Part A. Data will be reviewed on a cohort-by-cohort basis during the study until the MTD is determined. The purpose of these cohort-by-cohort reviews is to evaluate the safety data at each dose level and to determine if a DLT has been observed that would suggest MTD has been met or exceeded.

For Part B, both safety and efficacy data will be assessed. Interim analyses will be conducted after approximately 15 patients have completed 3 cycles in Parts B1,B2 and B4 (gastric, hepatocellular cancers and non-small cell lung cancer) and 6 cycles in Part B3 (renal cell cancer).

6.17. Planned Exploratory Analyses

Exploratory analysis will be performed to evaluate tumor tissue and blood for biomarkers related to the VEGF and MET signaling pathway and tumor biology of the respective tumor types enrolled in the study. Exploratory analyses may include but are not necessarily limited to tumor expression (eg, MET and VEGFR-2) and circulating biomarkers (eg, VEGF-A, HGF, extracellular cleaved domain of MET [MET ECD]) and their potential association with the objectives of the study (including PK/pharmacodynamic [PD] biomarker relationship).

Antitumor activity based on functional tumor imaging examinations (including but not limited to 2-deoxy-2[F-18]fluoro-D-glucose positron emission tomography (FDG-PET)) will also be analyzed exploratorily.

In the event of emergence of important and relevant scientific findings, SAP may be updated to allow further analyses on biomarkers and antitumor activities.

